The principal adverse events reported during the administration of MMF include diarrhea, leukopenia, sepsis, vomiting, and there is evidence of a higher frequency of certain types of infections eg, opportunistic infection. Elderly patients (≥ 65 years), particularly those who are receiving MMF as part of a combination immunosuppressive regimen, may be at increased risk of certain infections (including CMV tissue invasive disease) and possibly gastrointestinal hemorrhage and pulmonary edema, compared to younger individuals.

Adverse event profiles reported in the packaging insert for MMF are those described for solid organ transplant recipients who were treated with MMF as one of many treatments administered following surgical organ transplantation. By definition, these patients had

recent major surgery, end-stage organ failure for one or more organ systems, variable degrees of recipient organ tissue type mismatch, and were receiving combination immunosuppression with one or more concurrent medications. The relevance of these reports to the administration of MMF to patients with autoimmune disease such as SSc, in the absence of organ system failure and concurrent immunosuppressive therapy, is unknown.

Information that is more relevant to the patient population and intended use described in this protocol comes from SLS II, where patients with SSc-ILD with similar characteristics were randomized to receive either oral CYC for one year followed by Plac for a second year (N=73) or a two year course of oral MMF (N=69). Adverse event data comparing these two study groups is summarized as follows:

a) **Protocol defined and managed adverse events (AEs).** According to the protocol, five specific types of adverse events were pre-defined as likely to be related to the administration of study drugs and to warrant protocol-defined management.

- Anemia = Hgb <10.0 g/dl or <9.0 g/dl for those with Hgb <11.0 g/dl at enrollment
- Leukopenia = WBC <2.5x10³/μl
- Neutropenia = neutrophil count <1.0x10³/μl
- Thrombocytopenia = Platelet count <100.0x10³/μl
- Hematuria = >25 Red blood cells (or 10-15 range on more than one routine urine analysis) in absence of a urinary tract infection or menses

These protocol-defined AEs were tracked and recorded for all subjects until the time they either completed the study or withdrew or were withdrawn from active participation. The development of protocol-defined AEs from the SLS II study are summarized below by treatment arm.

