6.1.5 Pre-specified Dose Adjustment & Modifications

The toxicity profiles for MMF and PFD are well established as outlined in Section 2.3 and drug discontinuation and/or dose modification should be managed in a manner consistent with the following criteria in order to provide a nearly uniform response to pre-defined toxicity at all centers. However, in clinical situations that fall outside of these parameters and if warranted based on good clinical practice, a site investigator may independently modify drug dosing as needed to assure patient safety. If such a change is required, the reasons for the deviation are to be documented and the Executive Committee notified within 3 days. Medications that are contraindicated while on treatment with the study drugs are detailed separately in Section 7.5.

In the event that one study drug is permanently discontinued due to tolerability, adverse event or other medical consideration, then continued use of the remaining study drug will be according to the following pre-specified management:

- If only PFD/Plac is permanently discontinued, the participant may continue to take MMF according to the protocol and continue their participation in all study visits according to the normal protocol-defined schedule of events.
- If MMF is prematurely discontinued, the participant must stop the PFD/Plac study medication as well and will be asked to return for key outcome determinations at 12 and 18 months as detailed in Section 5.3.3 (Handling of Premature Participant Withdrawals).

6.1.5.1 Pre-specified dose adjustments for MMF.

The following abnormalities and laboratory test monitoring results require study drug adjustment, either temporary (until normalization) or permanent, as indicated by the nature of the event, its severity and/or course of resolution upon discontinuation of therapy.

- a) Allergic reaction associated with the administration of MMF.

Dose Management: Study drug will be stopped and subject withdrawn from study.

b) Evidence of clinically significant Bone Marrow Suppression including any one or more of the following

- WBC $<2.5 \times 10^3/\mu\text{l}$
- Absolute neutrophil count $<1.0 \times 10^3/\mu\text{l}$
- Platelet count $<100.0 \times 10^3/\mu\text{l}$
- Hemoglobin $< 10.0 \text{ gm/dl}$ or a drop in hemoglobin to $< 9.0 \text{ gm/dl}$ if the baseline hemoglobin was $< 11.0 \text{ gm/dl}$

Dose Management: Management as follows:

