- Hold study drug until there is a stabilization of the hematologic abnormality at a value above the toxicity threshold levels indicated above. In addition, if other causes of noted reductions are identified (e.g., gastrointestinal bleeding), they should be treated and stabilized before restarting on study drug.
- Once threshold levels are exceeded (an indication of recovery), MMF will be reintroduced at a daily dose of 1000 mg (500 mg twice daily doses) and increased by 500 mg (one 250 mg capsule for each of the twice daily doses) every two weeks. At the discretion of the clinical site investigator, after taking into account whether the study drug was likely or probably related to the adverse event, the final maintenance dose may be either the last regular dose of MMF taken by the patient or one capsule per-dose less (500 mg/day less).
- In the event of repeat toxicity, the same cycle should be repeated except with the intention of achieving a maintenance dose equal to 1000 mg/day less for MMF.

c) Documentation of gastrointestinal ulcer, bleeding or abdominal emergency.

Dose Management: Management as follows:

- Hold study drug until there is a clinically stable resolution of the problem. In addition, if other causes of noted conditions are identified (e.g., polyps, diverticulitis, untreated peptic ulcer disease), they should be treated and stabilized before restarting on study drug.
- Once a stable recovery occurs, as judged by the clinical site investigator, MMF will be reintroduced at a daily dose of 1000 mg (500 mg twice daily doses) and increased by 500 mg (one 250 mg capsule for each of the twice daily doses) every two weeks. At the discretion of the clinical site investigator, after taking into account whether the study drug was likely or probably related to the adverse event, the final maintenance dose may be either the last regular dose of MMF taken by the patient or one capsule per-dose less (500 mg/day less).
- In the event of repeat toxicity, the same cycle should be repeated except with the intention of achieving a maintenance dose equal to 1000 mg/day less for MMF.

d) Pregnancy or initiation of breastfeeding.

Dose Management: Study drug will be permanently discontinued and subject withdrawn from study.

e) Serum creatinine $> 2.0 \text{ mg/dl}$ or estimated GFR to $\leq 40 \text{ ml/min}/1.73 \text{ m}^2$ (corrected) in the absence of other etiology.

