8.2.4 AE of Special Interest

AEs meeting the following criteria will be classified and reported as AEs of Special Interest in addition to their inclusion in the overall frequency and incidence of AEs.

- Leukopenia, defined as $WBC \leq 2.5 \times 10^3/\mu\text{l}$ of blood
- Neutropenia, defined as an absolute neutrophil count $< 1.0 \times 10^3/\mu\text{l}$ of blood
- Clinically significant anemia, defined as blood hemoglobin $< 10.0 \text{ gm/dl}$ or a drop in hemoglobin to $< 9.0 \text{ gm/dl}$ if the baseline hemoglobin was $< 11.0 \text{ gm/dl}$
- Liver enzyme elevations that exceed $3 \times$ the upper limit of normal (ULN) ALT and/or AST.
- New onset or worsening of existing gastrointestinal symptoms that do not respond to medical management and are of sufficient clinical importance to warrant drug dose adjustment (including nausea, diarrhea, vomiting, and dyspepsia).
- Documentation of gastrointestinal ulcer, gastrointestinal bleeding or abdominal emergency
- Infection requiring hospitalization, intravenous antibiotics, or judged as requiring the withdrawal of immune suppression for effective treatment.
- New or reactivated viral infections including PVAN, JC virus associated PML, CMV infections, reactivation of HBV or HCV.
- Photosensitivity skin reactions that do not respond to sunscreen, avoidance, and as-needed use of over the counter topical creams, and are of sufficient clinical importance to warrant drug dose adjustment.
- Development of a proven malignancy other than basal cell cancer of the skin or cervical carcinoma in situ removed entirely by biopsy.
- Angioedema

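### The baseline-dependent clause of the anemia threshold has no effect as written, which leaves two readings for participants with baseline hemoglobin 10.0–10.9 g/dl

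*Protocol*

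**What the plan says.** Protocol 6.1.5.1(b) opens its list of MMF hold triggers with "Evidence of clinically significant Bone Marrow Suppression including any one or more of the following". The hemoglobin trigger is a value below 10.0 g/dl, with no baseline condition, "or a drop in hemoglobin to" below 9.0 g/dl "if the baseline hemoglobin was" below 11.0 g/dl. The consequence is "Hold study drug until there is a stabilization of the hematologic abnormality at a value above the toxicity threshold levels indicated above". After that, "MMF will be reintroduced at a daily dose of 1000 mg (500 mg twice daily doses) and increased by 500 mg" every two weeks.

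Protocol 8.2.4 repeats the two clauses for the AESI ("Clinically significant anemia, defined as blood hemoglobin" below 10.0, or the same conditional drop), and SAP 11.2.2 carries the same definition.

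Protocol 2.3.1.1.4 reports the SLS II definition as "Anemia = Hgb <10.0 g/dl or <9.0 g/dl for those with Hgb <11.0 g/dl at enrollment".

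Protocol 5.2.8(c) excludes only hemoglobin below 10.0 g/dl at screening, so participants at 10.0–10.9 g/dl can be enrolled.

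**The concern.** A clause that names a lower limit for participants who start low normally exists to change how they are handled. Here it cannot, because the first clause already captures everyone below 10.0. The SLS II wording ties the 9.0 limit to a subgroup, so a reader who knows that trial may apply 9.0 in place of 10.0 when baseline is below 11.0. A reader or programmer who follows the current text will apply 10.0 to everyone.

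Three things then depend on the reading: whether MMF is held, what value releases the hold, and whether the participant counts in the AESI anemia row. Protocol 6.1.5 says that its criteria are meant to give near-uniform handling of toxicity across centers, and a rule open to two readings works against that. Under 6.1.5.1(i), unresolved toxicity lasting 60 days or more ends MMF permanently. By 6.1.5 that also ends PFD/Plac, and follow-up then falls to the month 12 and 18 outcome visits.

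**Working it through.** The documents state no figure to reproduce. The check is one of logic, followed by an illustration on assumed inputs.

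**Step 1: is the second clause redundant?** Let H be on-study and B baseline hemoglobin, in g/dl.

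- As written: H < 10.0, or (H < 9.0 and B < 11.0).
- First clause alone: H < 10.0.
- Baseline-dependent reading: H < 9.0 if B < 11.0, otherwise H < 10.0.

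Take B from 10.0 to 18.0 (81 values) and H from 5.0 to 18.0 (131 values) in steps of 0.1. This gives 81 × 131 = 10,611 pairs. The rule as written and its first clause alone differ in 0 pairs, so the second clause is exactly redundant.

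**Step 2: where do the two readings part?** The written rule and the baseline-dependent reading differ in 100 pairs: the 10 baselines 10.0–10.9 crossed with the 10 on-study values 9.0–9.9. This locates the disagreement and says nothing about how often it occurs.

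**Step 3: smallest fall that counts.** As written it is B − 9.9. Under the other reading, for B below 11.0, it is B − 8.9.

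| Baseline | As written | Baseline-dependent reading |
|---|---|---|
| 10.0 | 0.1 | 1.1 |
| 10.5 | 0.6 | 1.6 |
| 10.9 | 1.0 | 2.0 |
| 11.0 | 1.1 | 1.1 |

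**Step 4: illustration only.** The documents give no within-person SD, so 0.3, 0.5 and 0.7 g/dl are assumed. Protocol 7.1.2.4 schedules 10 post-baseline counts (months 1–6, 9, 12, 15 and 18). Assume a stable true value equal to the recorded baseline b, independent normal draws with SD s, and results reported to 0.1 g/dl. The chance per count is p = Φ((c − b)/s), with c = 9.95 or 8.95. The chance of at least one event is 1 − (1 − p)^10. For example, b = 10.5 and s = 0.5 give p = Φ(−1.1) = 0.136 for a value below 10.0, hence 77%. For a value below 9.0, p = Φ(−3.1) = 0.0010, hence 1.0%.

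| True value | Below 10.0 at least once (SD 0.3 / 0.5 / 0.7) | Below 9.0 at least once (SD 0.3 / 0.5 / 0.7) |
|---|---|---|
| 10.0 | 99.7% / 99.8% / 99.8% | 0.2% / 16% / 50% |
| 10.5 | 29% / 77% / 91% | <0.1% / 1.0% / 13% |
| 10.9 | 0.8% / 25% / 60% | <0.1% / <0.1% / 2.6% |

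**Step 5: length of a hold's effect.** For a participant on 3000 mg/day who returns to that dose, the protocol's own steps give (3000 − 1000)/500 = 4 increments of two weeks, or 8 weeks, after the hold is released.

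**Step 6: which value is the baseline?** The schedules in the protocol summary and SAP 6.4 show a blood count at screening and none at V1. Protocol 5.2.8 also allows repeat testing within the screening period, so more than one pre-treatment value can exist. SAP 9.3 lists screening laboratory data among the baseline variables, which points to screening. Neither anemia definition says so.

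**The case against.** A reader might infer that the wording did turn trivial fluctuations into anemia events and drug holds. The documents do not show this. Nothing records which reading sites applied. The SLS II definition makes a baseline-dependent limit a plausible intent, and protocol 10.5.1 says that largely the same centers and investigators took part. The fall needed at baseline 10.9 (1.0 g/dl) is also close to the 1.1 g/dl needed at 11.0, so a description as small fluctuations does not fit the top of the band.

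A reader might also infer that the tolerability comparison is compromised. The tolerability endpoints in SAP 5.2.2 item 10 are time to withdrawal or removal from active drug, and participants with related treatment-emergent events by organ class. The AESI anemia count is neither; SAP 11 lists it as a descriptive safety summary. A temporary hold is not a removal, and the link to that endpoint runs only through the 60-day rule. The text is the same for both arms under blinding, so no direction of bias follows.

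The scale may be modest. In SLS II, 8 of 69 MMF patients (12%) had protocol-defined anemia at any baseline. If that rate carried over to the 51 patients indexed in SAP 10.1, about 6 would have it (51 × 8/69 = 5.9), and only some of those could be classified differently. Either count can also be derived later, since SAP 11.7 collects numeric hemoglobin.

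All of this stands. It limits the consequence and leaves the defect in place. A programmer following SAP 11.2.2 would code the literal rule even if sites had used the other, and the AESI table could then disagree with the recorded holds.

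**Conclusion.** The point holds as a defective threshold definition. The redundancy is exact and needs no assumption. The disagreement is confined to baseline 10.0–10.9 with on-study hemoglobin 9.0–9.9 g/dl, where the smallest qualifying fall differs by 1.0 g/dl between readings. It can affect MMF holds, release from holds and the descriptive AESI anemia count.

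How many participants are affected cannot be computed, because the documents give neither a baseline hemoglobin distribution nor a within-person SD. The crossing probabilities in the working are illustrations on assumed SDs and independent counts. With 51 patients split about evenly (an assumption), one reclassified participant moves an arm's proportion by roughly 4 percentage points (1/25). The primary endpoint's power and alpha are not affected. This review takes no position on which threshold is right.

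**What to change.** The sponsor should reconcile protocol 2.3.1.1.4, 6.1.5.1(b) (both the trigger and the release from a hold), 8.2.4 and SAP 11.2.2 to one unambiguous rule, and state which hemoglobin value is the baseline.

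SAP 14 records that enrollment stopped early, so the analysis steps matter most now. Before database lock:

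- specify in the SAP how the AESI anemia flag is programmed;
- tabulate the count by arm under both readings, from the numeric hemoglobin already collected;
- report which reading governed MMF holds at the sites.

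The cost is a wording change in the listed sections, one extra table and a check of hold records. No new data are needed.

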PML, which is sometimes fatal, commonly presents with hemiparesis, apathy, confusion, cognitive deficiencies, and ataxia. Risk factors for PML include treatment with immunosuppressant therapies and impairment of immune function. In immunosuppressed patients, physicians should consider PML in the differential diagnosis in patients reporting neurological symptoms and consultation with a neurologist should be considered as clinically indicated.

The risk of CMV viremia and CMV disease is highest among transplant recipients seronegative for CMV at time of transplant who receive a graft from a CMV seropositive donor. Therapeutic approaches to limiting CMV disease exist and should be routinely provided. Patient monitoring may help detect patients at risk for CMV disease.

Viral reactivation has been reported in patients infected with HBV or HCV. Monitoring infected patients for clinical and laboratory signs of active HBV or HCV infection is recommended.

- f) **Neutropenia.** Severe neutropenia [absolute neutrophil count (ANC) $<0.5 \times 10^3/\mu\text{L}$] developed in up to 2.0% of renal, up to 2.8% of cardiac, and up to 3.6% of hepatic transplant patients receiving MMF 3 g daily (see ADVERSE REACTIONS). Patients receiving MMF should be monitored for neutropenia. The development of neutropenia may be related to MMF itself, concomitant medications, viral infections, or some combination of these causes. If neutropenia develops (ANC $<1.3 \times 10^3/\mu\text{L}$), dosing with MMF should be interrupted or the dose reduced, appropriate diagnostic tests performed, and the patient managed appropriately. Neutropenia has been observed most frequently in the period from 31 to 180 days posttransplant in patients treated for prevention of renal, cardiac, and hepatic rejection. Patients receiving MMF should be instructed to report immediately any evidence of infection, unexpected bruising, bleeding or any other manifestation of bone marrow depression.

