7.2.6 Unscheduled Visits for Additional Safety Monitoring

As detailed in Protocol Section 8 on Safety, patients who experience defined adverse events that require additional safety monitoring will be asked to return at defined intervals for additional follow-up and blood test monitoring (if indicated). It is estimated that routine laboratory safety monitoring may be required every 1-2 weeks until the side effect is resolved or until a proper dose of medication is identified.

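### After a hold for ANC <1.0, Protocol 6.1.5.1 b lets MMF return to the full prior dose while ANC is still 1.0 to <1.3, where 2.3.1.1.3 f says to interrupt or reduce it

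*Protocol*

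**What the plan says.** Protocol 6.1.5.1 b makes an ANC below 1.0 x10³/µl one of four hematologic triggers for stopping MMF. The condition for ending the hold is: "Hold study drug until there is a stabilization of the hematologic abnormality at a value above the toxicity threshold levels indicated above". The restart rule is: "Once threshold levels are exceeded (an indication of recovery), MMF will be reintroduced at a daily dose of 1000 mg". The dose then goes up by 500 mg/day every two weeks. The investigator chooses the end dose after weighing whether MMF was a likely cause: "the final maintenance dose may be either the last regular dose of MMF taken by the patient or one capsule per-dose less". One capsule per dose is 500 mg/day. Repeat toxicity triggers the same cycle with a goal 1000 mg/day lower.

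Protocol 2.3.1.1.3 f, the summary of the MMF warnings, reads: "If neutropenia develops (ANC $<1.3 \times 10^3/\mu\text{L}$), dosing with MMF should be interrupted or the dose reduced".

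Scheduled counts (7.1.2.4) are monthly to month 6 and every three months after that. For defined adverse events, 7.2.6 estimates that safety laboratory tests "may be required every 1-2 weeks until the side effect is resolved or until a proper dose of medication is identified", and qualifies the extra blood tests as done where indicated. In clinical situations outside the listed criteria, 6.1.5 adds that "a site investigator may independently modify drug dosing as needed to assure patient safety".

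**The concern.** The level that ends the hold is the level that started it. From there the dose moves on a calendar, and the increase step names neither a blood count nor an ANC value. The warning section still regards a count below 1.3 as neutropenia that calls for interruption or a lower dose. A participant who has already fallen below 1.0, and who has recovered only to 1.0 to <1.3, can be taken back to the dose on which the fall occurred while following 6.1.5.1 b to the letter.

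At stake is avoidable repeat neutropenia and infection in a small number of participants. Nothing in this touches the primary endpoint, power or alpha.

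**Working it through.** The documents give no figure for this rule, so there is none to reproduce. The check sets the sections side by side, then sizes the problem.

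**1. ANC bands during re-titration.**
- Below 1.0: 6.1.5.1 b requires a hold. The warning is met.
- 1.0 to <1.3, dose below the prior dose: allowed by 6.1.5.1 b. The warning is met, because the dose is reduced.
- 1.0 to <1.3, full prior dose: allowed by 6.1.5.1 b. The warning is not met.
- 1.3 or above: no conflict.

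**2. Time to full dose.** Number of increases = (prior dose − 1000)/500, one every 14 days.
- Prior dose 2000 mg/day: 2 increases, 28 days.
- 2500 mg/day: 3 increases, 42 days.
- 3000 mg/day: 4 increases, 56 days.

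**3. Do scheduled counts cover this?** Up to month 6 they are 28 days apart and the steps 14 days apart, so not every step has one. After month 6 they are 3 × 28 = 84 days apart. If the hold lasts no more than 84 − 56 = 28 days, a full re-titration to 3000 mg/day can fit between two scheduled counts (visit windows ignored). Only the tests foreseen in 7.2.6 would then apply.

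**4. How many would enter the rule?** SLS II (2.3.1.1.4) recorded ANC <1.0 in 3 of 69 MMF patients over a two-year course: 3/69 = 4.35%, exact 95% CI 0.91% to 12.18%.
- Planned 150: 6.5 (1.4 to 18.3).
- The 51 indexed in the SAP 10.1 model: 2.2 (0.5 to 6.2).
- Scaled to 18 of 24 months, assuming a constant rate: 1 − (1 − 0.0435)^0.75 = 3.28%, giving 4.9 of 150 (1.0 to 13.9) or 1.7 of 51 (0.3 to 4.7).

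The documents do not say how many of these would stay at 1.0 to <1.3. The number affected runs from none to all of them.

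**5. Dose cost of stopping 500 mg/day short.** Per two weeks: 14 × 500 = 7,000 mg. Target exposure at 3000 mg/day is 504 × 3000 = 1,512,000 mg, so each two weeks costs 0.46%. Counting the initial titration, the target is 28 × (1000 + 2000 + 2500) + 420 × 3000 = 1,414,000 mg, and the cost is 0.50%.

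**The case against.** The strongest reply is that the rule already has safeguards. ANC <1.0 remains a hold trigger throughout, and a repeat event lowers the goal by 1000 mg/day. Restart needs a stabilized count, and the choice of end dose depends on judged causality, which fits the warning's own remark that neutropenia can have other causes. Section 7.2.6 plainly has re-titration in view. Items h and i of 6.1.5.1 cover other significant MMF-related events and toxicity unresolved for 60 days. SLS II recorded 3 neutropenia events in 3 MMF patients, so no repeats. The 1.3 level comes from labeling, and 2.3.1.1.4 says the relevance of the package-insert transplant adverse event profiles to SSc is unknown.

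Much of this stands and limits the point. It does not close the gap. A standing hold works only if the count is measured, and 7.2.6 foresees testing without requiring it or linking it to a step. The override is for situations outside the listed criteria, whereas re-titration after a hold is inside them. Causality, item h and item i set no ANC level. Three events are too few to show that repeats do not occur. On relevance, the same section says SLS II neutropenia on MMF occurred at rates seen in other indications.

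A reader might go further in two ways that the documents do not support. One is that no ANC condition applies to any increase; the <1.0 hold does. The other is that every increase should require ANC ≥1.3. Doses below the prior dose already satisfy the warning, and such a rule could keep a participant stable at ANC 1.2 on 1000 mg/day, one third of target, indefinitely.

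**Conclusion.** The point holds in a narrow form. Apart from the <1.0 hold and the lower goal after repeat toxicity, 6.1.5.1 b asks for no measured ANC before an increase and for no ANC above 1.0 before the full prior dose is regained. That end point conflicts with 2.3.1.1.3 f when ANC is 1.0 to <1.3. The intermediate steps and the 500 mg/day lower option do not.

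One might also infer that the <1.0 hold is itself wrong because the warning says 1.3. That is not concluded here: the warning section summarizes labeling, and SLS II used the same <1.0 definition for its managed events.

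The size is small: about 2 of 51 participants, or 6.5 of 150, would enter the rule, and an unknown share of them would be affected. This assumes that the MMF-alone rate from SLS II carries over to both arms. It may not for the combination, since 2.3.1.2.4 lists agranulocytosis among post-approval reactions to PFD. It is a cheap improvement for patient safety, not a threat to the trial's inference.

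**What to change.** Keep the <1.0 hold, the 1000 mg/day restart and the definition of neutropenia as an adverse event of special interest. Add to 6.1.5.1 b:

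> After a hold for neutropenia, obtain a CBC with differential within 7 days before each MMF increase; hold again if ANC is <1.0 x10³/µl. For a prior dose above 1000 mg/day, return to the last regular dose only if ANC is ≥1.3 x10³/µl; if ANC is 1.0 to <1.3, the maintenance dose is one capsule per dose less (500 mg/day less) until ANC is ≥1.3.

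The condition on the prior dose is there because 500 mg/day less than 1000 mg/day would fall below the protocol's own restart dose; that case stays as it is now.

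Cost: one paragraph, and up to 4 CBCs per affected participant plus repeats. At the unscaled SLS II rate that is 4 × 6.5 ≈ 26 counts for 150 participants, or 4 × 2.2 ≈ 9 for 51, largely foreseen by 7.2.6. MMF exposure falls by about 0.5% of target for each two weeks at the lower dose, and SAP 6.1 already accepts maintenance below target. No SAP change is needed. The SAP describes conduct in the past tense, so if no participant is still dosing, the edit serves only later use of this rule.
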